## Inclusion criteria - Individuals with MDD

*Participants will be men and women who:*

- Are aged 50 or older
- Able to read, write, and communicate in English
- Have a caregiver who is willing and able to provide the home tDCS sessions.
- Participants must be under the care of a treating psychiatrist who approves of the study participation and believes that TMS or ECT is indicated for his/her patient but that
  - it would not endanger the patient to participate in the present study rather than pursue such alternative, or
  - the patient could not gain access to TMS or ECT due to COVID-19

*(The depression phase of bi-polar disorder is not a reason for exclusion if the treating psychiatrist believes TMS or ECT would be indicated).*

Participants with MDD must fit into one of the following 3 groups (***medication-resistant MDD defined as 1) participant's condition has not responded to prescribed antidepressant medication; 2) participant is medication intolerant, or 3) some other underlying reason***):

- Patients with medication-resistant Major depressive disorder (MDD) who have undergone repetitive transcranial magnetic stimulation (rTMS) or electroconvulsive therapy (ECT) and responded to it but whose benefit has lapsed and they need repeat rTMS or ECT course that they cannot access;
- Patients with medication-resistant MDD who are undergoing rTMS or ECT and responding, but cannot continue to get the rTMS or ECT course due to COVID-19 pandemic-related regulations or other access concerns
- Patients with medication-resistant MDD who are referred to rTMS or ECT and are found well qualified but cannot access rTMS or ECT due to COVID-19 pandemic-related regulations or other access concerns.

Further, participants must:

- Meet criteria for a diagnosis of MDD according to the Diagnostic and Statistical Manual of Mental Disorders (DSM-IV-TR) (American Psychiatric Association, 2000), as determined via an tele-health interview with a study psychiatrist, and confirmed with the Mini International Neuropsychiatric Interview (MINI; Version 5.0.0) (Sheehan et al., 1998) and the prospective participant's primary psychiatrist.
- Currently experiencing a major depressive episode of at least four weeks' duration as part of a unipolar or bipolar depression. Score will need to be at least 20 on the MADRS.

Participant caregiver-administrators:

*Caregiver-administrators will be men and women, who may be a spouse, family member or friend who is*

- At least 21 years of age
- Able to read, write, and communicate in English
- Self-reported computer proficiency and willingness to learn how to use tDCS as defined by "yes" answers to the questions "Do you feel comfortable using a computer?" and "are you willing to learn
- How to administer tDCS?" Stated availability throughout the study period to administer tDCS sessions to

the participant with MDD.

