### **Study objectives:**

**Primary objective:** Demonstrate that remote tDCS sessions applied by a caregiver are feasible, complied and adhered to, and are safe in individuals with severe depression

**Secondary objective:** Gather pilot data on the potential of home-based tDCS to induce clinically meaningful improvements in the severity of depression in individuals who would otherwise be offered rTMS or ECT treatment.

The ultimate goal of this work is to prepare the path for a subsequent randomized clinical trial to assess the antidepressant therapeutic efficacy of home-based tDCS. We thus propose a study of tele-health supervised, caregiver-delivered, home-based tDCS for antidepressant treatment of patients with a medication-resistant depression episode of uni- or bi-polar Major Depression who would otherwise qualify for rTMS or ECT.

Specifically, in the present protocol we seek to offer participation to:

- Patients with medication-resistant MDD who have undergone rTMS or ECT and responded to it but whose benefit has lapsed, and they need repeat a rTMS or ECT course that they cannot access
- Patients with medication-resistant MDD who are undergoing rTMS or ECT and responding, but cannot continue to get the rTMS or ECT course due to COVID-19 pandemic-related regulations or other access concerns
- Patients with medication-resistant MDD who are referred to rTMS or ECT and are found well qualified but cannot access rTMS or ECT due to COVID-19 pandemic-related regulations or other access concerns.

The benefits of this project address a present need due to the COVID-19 pandemic, but also go beyond the present situation and address a larger, pre-existing need.

Across all these potential groups of participants, prospective participants will:

1. Need to have a primary psychiatrist who agrees to their participation in the study and is willing to continue to follow the patient and work collaboratively with the study team
2. Need to be assessed by their primary psychiatrist to be stable enough to be able to remain at home and participate in the present study without undue risk to their safety
3. Need to be living with an adult willing and capable to provide oversight and learn to deliver the home-based tDCS
4. Have the capability to connect with the study team for daily supervision of the intervention sessions and close safety monitoring, and be willing to commit to doing so

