In the setting of depression, Clayton et al., (2018) reported a case of one patient with comorbid multiple sclerosis and recurrent depressive episodes who received a course of remotely supervised tDCS following ECT treatment. Fatigue and mood ratings improved. More recently, Alonzo et al. (2019) completed a proof-of-principle, open-label trial in 34 participants who were taught to self-administer 20–28 tDCS sessions (2 mA, 30 min, F3-anode and F8-cathode montage according to 10–20 EEG placement) over 4 weeks followed by a taper phase of 4 sessions 1 week apart. Participants were initially monitored via video link for a few days, and then through completion of an online treatment diary. Participants met criteria for a diagnosis of MDD according to the DSM-IV-TR, as determined via an interview with a study psychiatrist, and confirmed with the Mini International Neuropsychiatric Interview (MINI; Version 5.0.0) (Sheehan et al., 1998). Inclusion criteria included a current major depressive episode of at least four weeks duration as part of a uni- or bipolar depression; and a score of at least 20 on the Montgomery–Asberg Depression Rating Scale (MADRS) at trial entry. Exclusion criteria were any DSM-IV-TR psychotic disorder; drug or alcohol abuse or dependence in the preceding 3 months; concurrent benzodiazepine medication; high suicide risk; history of clinically defined neurological disorder or insult; metal in the cranium or skull defects; skin lesions on the scalp at the proposed electrode sites; and pregnancy. Participants on antidepressant medication were permitted to enter the trial provided the medication dose was unchanged for 4 weeks prior to trial entry and during the acute treatment phase of the study. One participant was withdrawn from the study due to too many missed sessions. The remaining 33 participants completed 93% of the scheduled sessions in the initial 4-week phase. Ten of thirteen participants (77%) who qualified for the maintenance phase opted to continue. Mood improved significantly from baseline (27.5 on MADRS) to 1 month after the end of acute treatment (MADRS 15.5;  $p < 0.001$ ). Side effects reported across a total of 1,149 sessions were minimal, primarily mild to moderate tingling or burning/heat sensation during stimulation and redness at the electrode sites. This study provides clear, initial evidence that home-based, remotely supervised tDCS treatment is feasible for depressed patients and offers a potentially effective intervention.

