### Exclusion criteria for participants with MDD will be:

- Any DSM-psychotic disorder
- Drug or alcohol abuse or dependence in the preceding three months;
- Concurrent benzodiazepine medication;
- High suicide risk (*Utilizing the Beck Depression Inventory and the Hamilton Depression Scale, suicide risk will be assessed at baseline by the study psychiatrist*) ;
- History of clinically defined neurological disorder or insult; Metal in the cranium or skull defects;
- Skin lesions on the scalp at the proposed electrode sites;
- Pregnancy.
- Medical devices (i.e. cardiac pacemaker, deep brain stimulator, medication infusion pump, cochlear implant, vagus nerve stimulator).
- Previous skull surgery with resultant skull defects
- Inability to understand study procedures following review of the Informed Consent form.

Understanding will be assessed by asking the participant with MDD to answer the following three questions:

- 1) What is the purpose of this study?
- 2) What are the risks of study involvement?
- 3) If you decide to participate, are you allowed to withdraw from the study at any time?

Answers will be recorded by study personnel on the "Assessment of Protocol Understanding" form. Insufficient understanding will be defined by one or more incorrect answers, as determined at the discretion of the investigator.

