Wks 1-4, D 7, 14, 21, and 28	Weekly assessments	Participants with MDD only Week 1-4 Assessment completion (Day 7, 14,21, and 28); depression symptoms and quality of life assessments	Study research assistant	30 minutes	Phone
Home tDCS administration Treatment taper period – weeks 5-8 Participant ratings of suicidality will be completed each day, and responses will be monitored and immediately be reviewed in real time by the study RA and study psychiatrist. Any changes from baseline will result in an immediate contact to the participant by the study psychiatrist.					
Wk 5, D 30,32,34	Home-based tDCS Total of 3 sessions, one every other day over a 6 day period.	The caregiver-administrator will administer the in-home tDCS session with remote staff monitoring and video conferencing if necessary Daily diary	Study research assistant	1 hour	Participant's Home
Wk 6-7, D 37,40, 43	Home-based tDCS Total of 3 sessions, one every third day over a 9 day period	The caregiver-administrator will administer the in-home tDCS session with remote staff monitoring and video conferencing if necessary Daily diary	Study research assistant	1 hour	Participant's Home
Wk 8 D 47,51, 55	Home-based tDCS Total of 3 sessions, one every fourth day over a 12 day	The caregiver-administrator will administer the in-home tDCS session with remote staff monitoring and video conferencing if necessary Daily diary	Study research assistant	1 hour	Participant's Home

	period				
Wks 5-8 D35, 42, 49, 56	Weekly assessments	Participants with MDD only Weeks 5-8 Assessment completion (Day 35, 42,49, and 56); depression symptoms and quality of life assessments	Study research assistant	30 minutes	Phone
Home tDCS administration completed after Week 8, Day 55 session. Return of Home tDCS equipment to research team in the provided shipping materials and label.					
Four week follow-up period – weeks 9-12					
Wks 9- 12 D57-84	Four week follow-up period	Participants with MDD only The study research assistant will maintain weekly contact with the participant over the 4 week follow-up period	Study research assistant	20 minutes	Phone
Week 12, Day 84	Final study assessment	Both participants: Final assessment completion, depression symptoms, quality of life assessments, cognitive assessment	Study research assistant	1 hour	Phone
End of study: Results sent to participant with MDD and treating psychiatrist					

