## Statistical Methods and Analysis

### *Primary*

Feasibility and tolerability/safety will be evaluated using home-based data as it is collected by reported number of aborted sessions.

The *primary outcome* will be change in the observer rated MADRS score from baseline to the 1-month follow-up.

Clinical response is defined as  $\geq 50\%$  improvement in MADRS score from baseline to the 1-month follow-up. Remission is defined as a MADRS score  $\leq 10$ .

The *secondary outcome* measures will include the participant-rated Quick Inventory of Depressive Symptomatology (QIDS-SR) (Rush et al., 2003) and the Quality of Life Enjoyment and Satisfaction Questionnaire Short Form (Q-LES-Q-SF) (Endicott et al., 1993), both administered at the same time points as the MADRS. A computer-based cognitive test battery, CogState (<https://www.cogstate.com>), will provide an additional safety outcome measure. This battery includes tests designed to assess verbal learning and memory (International Shopping List Task), attention and psychomotor function (Detection Task), visual attention (Identification Task), visual learning and memory (One Card Learning Task), working memory (Two Back Task), and executive function (Set Shifting Task).

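### Bipolar depression is admitted, but no mania or hypomania rating is named and response and remission rest on the MADRS alone, so a participant who has switched could be counted as a success

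*Combined protocol and SAP*

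**What the plan says.** Bipolar depression is admitted deliberately. Study objectives describes the target population as "patients with a medication-resistant depression episode of uni- or bi-polar Major Depression who would otherwise qualify for rTMS or ECT". The inclusion criteria for individuals with MDD add that "The depression phase of bi-polar disorder is not a reason for exclusion if the treating psychiatrist believes TMS or ECT would be indicated", and require a current episode "as part of a unipolar or bipolar depression. Score will need to be at least 20 on the MADRS". No cap or stratum is set for bipolar participants. The nearest exclusion is "Any DSM-psychotic disorder"; none mentions mania or hypomania.

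Under Statistical Methods and Analysis (Primary), the primary outcome "will be change in the observer rated MADRS score from baseline to the 1-month follow-up"; the Primary Analysis Plan for efficacy expresses it as a median percentage change. Response is a MADRS improvement of at least half by the 1-month follow-up. "Remission is defined as a MADRS score" of 10 or less, with no time point attached. The secondary outcomes are the QIDS-SR (depressive symptoms) and the Q-LES-Q-SF (quality of life), and CogState is an additional safety measure of cognition.

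In the Visits table, the weekly assessments on Days 7 to 56 cover "depression symptoms and quality of life assessments", and Day 84 adds cognition. Suicidality is rated daily through week 8, and a diary accompanies the sessions. Weeks 9 to 12 have weekly research-assistant calls whose content is not described.

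**The concern.** The MADRS and QIDS-SR measure one pole of mood. In a bipolar participant, a low depression score can mean recovery or a change of phase, and these scales cannot tell the two apart. Nothing in the response or remission definitions separates them either, so an unwanted event could be entered as a favourable result.

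Two things are at stake. First, Study objectives makes safety part of the primary objective; with no scheduled measure, the study cannot report a switch rate for the bipolar patients whom it chose to enrol. Second, the pilot data are meant to prepare a randomized trial, and response and remission are the two binary summaries that the plan defines. With a single arm, no comparison group would carry the same misclassification and offset it.

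**Working it through.** **Step 1. Is the opposite pole measured anywhere in the visible text?**

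| Place | What is named | Mania or hypomania? |
|---|---|---|
| Primary and secondary outcomes | MADRS, QIDS-SR, Q-LES-Q-SF | No |
| Additional safety outcome | CogState | No (cognition) |
| Daily rating, weeks 1-8 | Suicidality | No |
| Weekly assessments, Days 7-56 | Depression, quality of life | No |
| Day 84 | Depression, quality of life, cognition | No |
| MINI | Confirms diagnosis at entry | Not repeated in the visit table |
| List of assessments and forms | No mania scale by name | Contents of the side-effects form not shown |
| Daily diary | Named only | Contents not shown |

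The words mania and hypomania do not appear in the documents.

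**Step 2. Would one low score satisfy both definitions?** Entry requires a MADRS of at least 20. Taking that as the baseline, a score of 10 or less is a fall of at least (20 - 10)/20 = 50%, and more from a higher baseline. A single score of 10 or less at the 1-month follow-up therefore meets both definitions, with no condition on why it is low. Recording an adverse event does not alter the count, because no rule links the two.

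**Step 3. Size per participant.** The sample size is 50 (Sample Size section, with no derivation to reproduce). One misclassified participant is 1/50 = 2 percentage points; two are 4. For scale, the meta-analytic rates on active tDCS cited in the section on tDCS and depression give 0.309 x 50 = 15.45, about 15 responders, and 0.199 x 50 = 9.95, about 10 remitters. One participant is then 1/15 = 6.7% of responders or 1/10 = 10% of remitters.

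**Step 4. How likely is it?** The documents give neither the bipolar share nor a switch rate. Assumptions: a bipolar share of 10% to 40% (n = 5 to 20) and a switch rate s of 2% to 10%. Expected switches = n x s; chance of at least one = 1 - (1 - s)^n.

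| Bipolar n | s = 2% | s = 5% | s = 10% |
|---|---|---|---|
| 5 | 0.1; 9.6% | 0.25; 22.6% | 0.5; 41.0% |
| 10 | 0.2; 18.3% | 0.5; 40.1% | 1.0; 65.1% |
| 15 | 0.3; 26.1% | 0.75; 53.7% | 1.5; 79.4% |
| 20 | 0.4; 33.2% | 1.0; 64.2% | 2.0; 87.8% |

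If every switch counted as a response that would not otherwise have occurred, the rate would rise on average by between 0.1/50 = 0.2 and 2.0/50 = 4.0 percentage points. That is an upper limit within these assumptions.

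**Step 5. Effect on the primary measure.** With 50 values the median lies between the 25th and 26th in order. Changing k values moves it by at most k ranks, so one or two switches shift it by one or two ranks at most.

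**Step 6. What measurement would add for safety.** With a scheduled rating and no switch seen, the exact one-sided 95% upper bound on the switch rate is 1 - 0.05^(1/n): 45.1% for n = 5, 25.9% for n = 10, 18.1% for n = 15 and 13.9% for n = 20. These bounds are wide, but without systematic ascertainment an absence of reported switches supports no bound.

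**The case against.** The strongest reply is that the trial is closely watched. The study psychiatrist reviews the daily suicidality ratings in real time through week 8, and any departure from baseline prompts contact. There is a diary, remote monitoring of sessions, an observer-rated MADRS, weekly contact to week 12, a caregiver living with the participant, and a treating psychiatrist who keeps following the patient. A change in clinical condition brings the two psychiatrists into contact (Risks), a clinician's judgement of marked worsening stops stimulation (Stimulation Stopping criteria), and the adverse event definition is broad enough to include mania.

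Most of this stands. A reader might infer that a switch would surface only if someone volunteered it, or that clinicians are largely absent after the first week; the documents support neither. Nor do the published side effects under Adverse Events show what is collected: a separate side-effects questionnaire is listed, and its contents, like the diary's, are not shown. An incidental item on elevated mood cannot be ruled out.

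What the reply does not reach is the endpoint. None of these routes is specific to mania, the daily ratings end with week 8, and none feeds into response or remission. A switch recognised and recorded through any of them could still be counted as remission.

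It is also fair that the primary measure is a median, that significance is explicitly not a goal, and that the Statistics section plans no analysis of response or remission. This limits the consequence, but the plan defines both outcomes, and the definitions should mean what a reader will take them to mean.

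**Conclusion.** The point holds as a gap in the definitions and in safety measurement, and it is worth a cheap correction. Its effect on the primary median is small; on response or remission it is 2 percentage points per misclassified participant, with 0.1 to 2.0 switches expected under the assumed ranges in Step 4. Those ranges are illustrations, since the documents supply neither input.

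Three stronger readings are tempting and are not supported. A switch does not guarantee a low MADRS: the definitions leave the misclassification open, and the score would have to be low at the 1-month follow-up. If that is Day 84, it falls 84 - 55 = 29 days after the last session. The documents do not say that tDCS causes switching; they do not discuss it. And the primary result is not undermined. The conclusion rests on the visible text, with the contents of the diary and the side-effects form unknown.

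**What to change.** In the Visits table, add a short self-report mania/hypomania scale to the existing weekly assessments and to Day 84, at least for participants with bipolar depression, and name the scale in the list of forms. Self-report suits calls made by a research assistant; repeating MINI items might need qualified raters.

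Under Statistical Methods and Analysis (Primary), state that a participant who meets the scale's pre-set threshold, or has a recorded manic or hypomanic episode, at the endpoint assessment is not counted as a responder or remitter. State also that switches are reported as a separate safety outcome. Showing MADRS change separately for unipolar and bipolar participants would not replace this, because it leaves the misclassification in place.

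The clinical handling of a switch stays with the study clinicians. The cost is slightly longer calls, one more form, a few sentences of text, and possibly slightly lower response and remission rates.

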### Exclusion criteria for participants with MDD will be:

- Any DSM-psychotic disorder
- Drug or alcohol abuse or dependence in the preceding three months;
- Concurrent benzodiazepine medication;
- High suicide risk (*Utilizing the Beck Depression Inventory and the Hamilton Depression Scale, suicide risk will be assessed at baseline by the study psychiatrist*) ;
- History of clinically defined neurological disorder or insult; Metal in the cranium or skull defects;
- Skin lesions on the scalp at the proposed electrode sites;
- Pregnancy.
- Medical devices (i.e. cardiac pacemaker, deep brain stimulator, medication infusion pump, cochlear implant, vagus nerve stimulator).
- Previous skull surgery with resultant skull defects
- Inability to understand study procedures following review of the Informed Consent form.

Understanding will be assessed by asking the participant with MDD to answer the following three questions:

- 1) What is the purpose of this study?
- 2) What are the risks of study involvement?
- 3) If you decide to participate, are you allowed to withdraw from the study at any time?

Answers will be recorded by study personnel on the "Assessment of Protocol Understanding" form. Insufficient understanding will be defined by one or more incorrect answers, as determined at the discretion of the investigator.

### Exclusion criteria for Participant caregiver-administrators:

- Poor eyesight,
- Severe arthritis in the hands, pain, deformity or other condition that interferes with successful administration of tDCS.
- Inability to understand study procedures following review of the Informed Consent form.

Understanding will be assessed by asking the participant caregiver-administrator to answer the following three questions:

- 1) What is the purpose of this study?
- 2) What are the risks of study involvement?
- 3) If you decide to participate, are you allowed to withdraw from the study at any time?

Answers will be recorded by study personnel on the "Assessment of Protocol Understanding" form (see attached). Insufficient understanding will be defined by one or more incorrect answers, as determined at the discretion of the investigator

